## 7.4. Dose Modification

### 7.4.1. Dose Decision (Part C)

The decision to initiate the first patient cohort in Part C will be based on the trial-level safety review for Cohort 3; however, any available preliminary PK data from Cohorts 1, 2, and 3 (through Day 29) in Part A will be considered as well. Progression to the optional cohorts in Part C will occur when at least 4 weeks of clinical activity data (PASI scores) are available from at least 7 patients in the preceding cohort. In addition to the PASI scores, any available PK and applicable safety data from Part A will be considered for determining the dose for the optional patient cohorts. Dosing at the current level and further dose escalation will be discontinued if any of the scenarios described in Section 7.4.2 occur.

CCI

### 7.4.2. Dose Escalation (Parts A and B)

By nature of being a dose-escalation study, data will be evaluated on an ongoing basis. The highest dose level that is tolerated will be designated as the MTD.

Safety data will be the primary criteria for the dose escalation. In addition, if available at the time of dose-escalation decision, PK results ( $C_{max}$  and AUC) will be used as supporting data for dose escalation, but such data are required only for Cohort 1 in Part B. No dose decision can occur without prior discussion and agreement between the investigator and the Lilly clinical pharmacologist or CRP.

Prior to dose escalation, a safety review meeting will be undertaken by the sponsor (unblinded) and the investigator (blinded) to evaluate the safety data and agree on the appropriate dose for the next cohort. Emerging PK data (if available) may inform dose selection for the higher dose levels, based on planned PK preliminary analyses after SAD Cohort 3 (Part A). If considered appropriate, previous dose levels may be repeated, or lower/intermediate dose levels may be

tested. The magnitude of the dose escalation may be reduced after data review, but subsequent escalations cannot be increased by more than approximately 3-fold (a half-log increment).

For Cohorts 1 and 2 in Part A, the decision to escalate to the next cohort will occur when at least 15 days have elapsed after all subjects in the preceding cohorts have been dosed. In Cohorts 3, 4, 6, and 7, the decision to dose the next cohort will occur when all subjects in the preceding cohorts have been dosed and data for a minimum of 15 days are available from at least 7 subjects in the preceding cohort. If at the time of the trial level safety review for Cohort 4, data are also available from Cohort 5, all available data from Cohorts 4 and 5 will be considered in the review to dose the next cohort.

The decision to initiate the first multiple-dose cohort in Part B will occur when at least 15 days have elapsed after all subjects in the last cohort in Part A have been dosed (Cohort 7 unless safety concerns prevent escalation to this cohort). The trial-level safety review for all previous cohorts and the preliminary analyses of PK data (planned to occur after the completion of Day 29 for Cohort 3) will be considered in the decision to initiate Part B of the study. Progression to the optional cohort in Part B will occur when all subjects have received the second dose of study drug and data for a minimum of 15 days (after the second dose) are available from at least 7 subjects in Cohort 1 of Part B.

Throughout Part A and Part B, safety data up to and including Day 15 are required for dose-escalation decisions. If any subjects withdraw before the Day 15 assessment, all available safety data for those subjects will be evaluated.

Safety data, in particular AEs, SAEs, and adverse laboratory abnormalities, will be independently assessed by the investigator, and will be considered related to the IP unless there is clear evidence that the event is not related.

After review of these data, an agreement on the appropriate dose will be made by the investigator and sponsor for the next cohort/dose level. The magnitude of dose escalations may be reduced following data review, but subsequent escalations cannot be increased by more than approximately 3-fold (a half-log increment).

If any of the following scenarios occur, dosing at the current level and further dose escalation will be discontinued:

A single patient/subject experiences an SAE or clinically significant event that is related to LY3316531 administration

OR

Two or more patients/subjects develop AEs within 14 days of dosing that are considered to be related to study treatment and graded as at least moderate, clinically significant, and not responsive to supportive care

OR

One or more patients/subjects develop AEs within 14 days of dosing that are considered to be related to study treatment and graded as severe

OR

Two or more subjects develop AEs that are graded as severe, unless there is an obvious explanation other than IP or study procedures for the event(s)

OR

After the introduction of premedication in accordance with the protocol, 2 or more patients/subjects develop (according to Common Terminology Criteria for Adverse Events)  $\geq$ Grade 2 acute AEs related to the infusion, during or within 2 hours of completing the infusion that do not resolve with a reduced infusion rate and/or supportive care.

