### Treatment Arms and Planned Duration for an Individual Patient/Subject:

**Part A (Single-Ascending Dose [SAD] in Healthy Subjects):** After a screening period up to 28 days, eligible subjects will be randomized to receive a subcutaneous (SC) or intravenous (IV) dose of LY3316531 (3 mg IV, 15 mg IV, 75 mg IV, 300 mg IV, 300 mg SC, 900 mg IV, or 2000 mg IV [planned dose]) or placebo (IV) on the morning of Day 1. Subjects will remain in the CRU for 24 hours after study drug administration and attend scheduled visits at the CRU for 12 weeks to assess the measurements for safety, tolerability, and PK. Sentinel dosing for the first 2 subjects of Cohorts 1 and 2 will be performed with 1 subject receiving LY3316531 and the other receiving placebo in a blinded manner.

**Part B (Multiple-Dose in Healthy Subjects):** After a screening period up to 28 days, eligible subjects will be randomized to receive a planned IV dose of LY3316531 (2000 mg [planned dose]) or placebo on the morning of Days 1, 29, and 57. The planned dose of 2000 mg LY3316531 may be adjusted based on safety, PK, and target-engagement data obtained in Part A of the study. An optional SC or IV second multiple-dose cohort will be determined after reviewing the data from the first cohort.

Subjects will remain in the CRU for 24 hours after receiving each dose of study drug and attend scheduled visits at the CRU for 12 weeks following the final (third) dose of LY3316531 to assess the measurements for safety, tolerability, and PK.

**Part C (Single-Dose in Patients with Psoriasis):** After a screening period up to 35 days, eligible patients with psoriasis will be enrolled to receive a single dose of LY3316531 on the morning of Day 1. Patients will receive 300 mg IV in Cohort 1 or, in the 2 optional cohorts, receive either a SC or IV dose (to be determined) not to exceed the maximum tolerated dose in Part A or the highest dose previously evaluated in healthy subjects. Patients will remain in the CRU for 24 hours after study drug administration and attend scheduled visits at the CRU for 16 weeks following administration of the study drug to assess the measurements for safety, tolerability, PK, and PD. Patients who respond to LY3316531 therapy will enter an extended follow-up period, which requires monthly visits up to Week 52. Patients who enter the extended follow-up period should be discontinued from the study when additional therapy becomes necessary (as determined by the investigator and patient).

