**Figure FFAA.5.1. Illustration of study design for Protocol I9H-MC-FFAA.**

### 5.1.1. Part A (SAD in Healthy Subjects)

Seven planned dose-escalation cohorts will be enrolled to receive either IV or SC administration of LY3316531 (3, 15, 75, 300, 900, or an additional dose not to exceed 2000 mg) or placebo.

Sentinel dosing will be used in Cohorts 1 and 2 to minimize the risk to subjects receiving this novel antibody. Initially, 2 subjects (1 receiving LY3316531 and 1 receiving placebo) will be dosed in a blinded manner (sentinel subjects) and these subjects will be followed for at least 24 hours postdose before the remaining subjects in that cohort are dosed (subject blind only). The remaining subjects may then be dosed on the same day or subsequent days (but not necessarily consecutive days), as determined by the investigator. Dose escalation to the next cohort can begin after a safety review of data from the preceding cohort (see Section 7.4.2 for a more detailed description). All 6 subjects in Cohort 5 will receive 300 mg of LY3316531 SC.

All subjects who meet eligibility criteria will be followed for 12 weeks post-treatment administration. A subject's participation is considered as complete if he/she received the study drug and completes all activities up to and including at least Day 57. Subjects may be replaced if PK data are not collected up to and including Day 57.

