#### ***10.3.5. Data Review During the Study***

Access to safety data is scheduled to occur after every dosing session. The purpose of these reviews is to guide dose selection for the next dosing session, and/or to inform the design of subsequent studies. The investigator and the Lilly sponsor team will make the determination regarding dose escalation, based upon their review of the data. The investigator will remain blinded, and the Lilly sponsor team will be unblinded during these reviews.

In addition, data snapshots for preliminary analyses of PK data are planned to occur after Day 29 of Cohort 3 (Part A) prior to the initiation of the multiple-dose cohorts (Part B). The evaluation of these data will aid in determining the dose, margin of safety, and adjustment of PK sampling schedule. Data snapshots are also planned to occur after Day 29 of Cohort 6 in Part A and Day 57 of Cohort 1 in Part B. Additional data snapshots may be conducted as required. These snapshots and analyses will be conducted while the trial is ongoing, but no changes to the study design are planned.

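### Does the 3-fold limit on escalation in Protocol Section 7.4.2 forbid the first three planned dose steps?

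*Protocol*

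**What the plan says.** Section 7.4.2 of the Protocol (Dose Escalation, Parts A and B) gives the limit twice. The first statement is "The magnitude of the dose escalation may be reduced after data review, but subsequent escalations cannot be increased by more than approximately 3-fold". The second, later in the section, is "The magnitude of dose escalations may be reduced following data review, but subsequent escalations cannot be increased by more than approximately 3-fold". Both add that this means a half-log step. The sentence just before the first statement deals with departures from the planned ladder: "previous dose levels may be repeated, or lower/intermediate dose levels may be" tested if that is thought appropriate.

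The planned doses are listed in several places. The synopsis gives "3 mg IV, 15 mg IV, 75 mg IV, 300 mg IV, 300 mg SC, 900 mg IV, or 2000 mg IV". Section 5.1.1 gives "LY3316531 (3, 15, 75, 300, 900, or an additional dose not to exceed 2000 mg", and SAP Section 5.1 lists the same levels. Protocol Table FFAA.5.1, SAP Table 1 and SAP Section 6 agree with them. The SAP does not repeat the fold limit.

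On the timing of reviews, Section 5.1.1 says "Dose escalation to the next cohort can begin after a safety review of data from the preceding cohort", and Section 10.3.5 says "Access to safety data is scheduled to occur after every dosing session".

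**The concern.** Put the limit beside the ladder and they seem to clash. The first three IV steps are 5-fold, 5-fold and 4-fold, and the text says that later steps cannot exceed about 3-fold. Because the limit is tied to a half-log, *approximately* can hardly stretch to 4 or 5.

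The words about data review do not obviously rescue the ladder, because every escalation in this study follows a data review. If *subsequent* meant any escalation after a review, Section 7.4.2 would forbid steps that the synopsis, Section 5.1.1 and Table FFAA.5.1 all plan.

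This is a first-in-human study, and the sentence is the only fold limit on step size in the visible text. Two parties who must agree each dose could in principle read it differently.

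**Working it through.** **Inputs.** Planned IV doses in Part A (synopsis; Table FFAA.5.1; SAP Table 1): 3, 15, 75, 300, 900 and 2000 mg. Cohort 5 (300 mg SC) repeats the 300 mg level by another route and adds no dose step. Limit (Section 7.4.2): about 3-fold, equated with a half-log.

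**The plan's own figure.** Half-log = 10^0.5 = 3.16, which agrees with *about 3-fold*.

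**Step sizes.** Step = next dose / preceding dose.

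| Step (mg) | Ratio | Against 3.16 |
|---|---|---|
| 3 to 15 | 15/3 = 5.00 | 5.00/3.16 = 1.58, 58% above |
| 15 to 75 | 75/15 = 5.00 | 58% above |
| 75 to 300 | 300/75 = 4.00 | 4.00/3.16 = 1.26, 26% above |
| 300 to 900 | 900/300 = 3.00 | within |
| 900 to 2000 | 2000/900 = 2.22 | within |

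**Planned steps over the limit, by reading of *subsequent*.**

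1. *Steps that follow a data-driven reduction or other departure from the ladder:* 0 of 5. A ladder given as planned contains no such step.
2. *Every escalation that follows a data review:* 3 of 5.
3. *Steps after the Cohort 3 pharmacokinetic review:* 1 of 3 (75 to 300 mg). The text on that review is a separate sentence saying that the data may inform dose choice. It sets no fold limit.
4. *Steps from 300 mg upward:* 0 of 2. Nothing in the limit sentence points to 300 mg.
5. *A limit on growth of the step multiple itself:* the successive ratios of multiples are 5/5 = 1.00, 4/5 = 0.80, 3/4 = 0.75 and 2.22/3 = 0.74. All comply, although the half-log gloss fits a dose step better than a change in the multiple.

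**Choosing between them.** Three features of the text favour reading 1.

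- The sentence has two linked halves: a step may be made smaller, *but* later ones are bounded. The *but* ties the bound to the reduction.
- In its first appearance the sentence comes directly after the one on repeated, lower or intermediate levels, so the topic is already departure from plan.
- Reading 2 makes a general clause cancel doses that the same protocol lists by name, and it leaves the word *subsequent* with little to do.

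Reading 1 still gives the limit work to do: after an intermediate level, in choosing the flexible top dose in Section 5.1.1, and possibly in the optional Part B cohort, whose dose is undetermined.

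**The case for a change.** The best opposing argument is that a rule saying *cannot* should state its scope, and the visible text of this one does not. Even on the favoured reading two questions stay open. Section 7.4.2 allows a level to be repeated without saying whether a repeat counts as a reduction. If it does, a repeat of 15 mg or 75 mg would put the next planned step, 5-fold or 4-fold, over the limit. And because *subsequent escalations* is plural, it is unclear whether one early reduction binds only the next step or all later ones. The other safeguards do not say which steps the limit governs. Sentinel dosing covers Cohorts 1 and 2 only, so of the three large steps just the first leads into a sentinel cohort.

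These points stand as remarks on wording. They arise only if the trial leaves its planned course, and there Section 7.4.2 already requires a safety review and agreement between investigator and sponsor before any dose decision. The open questions would be settled at that meeting.

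Parts of Sections 5.5 and 7.4.1 are blacked out and the design figure is not shown. A statement on step size could sit there, so its absence from the visible text cannot be held against the plan.

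**Conclusion.** The arithmetic behind the concern is right: three of the five planned IV steps are larger than a half-log. A contradiction is not shown, because on the natural reading of Section 7.4.2 none of the five is governed by the limit. The conflict appears only if the limit is stretched to cover planned steps, and the protocol's own list of doses tells against that.

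What remains is a small gap in wording that those running the study would fill sensibly. A team following the plan would give the listed doses, subject to the Day 15 safety reviews, joint dose agreement, stopping scenarios and 2000 mg ceiling. All of these hold on any reading. No endpoint, analysis population or estimate depends on the scope of the limit, and the dose-proportionality model in Section 10.3.2.2 can be fitted to whatever IV doses are given. Stating the scope would change no planned dose and no conclusion.

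This rests on two assumptions: that *subsequent* refers back to the reduction in the same sentence, and that no hidden text says otherwise. It takes no view on which dose, step size or limit is right.

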### **7.4.3. Special Treatment Considerations**

Premedication for the infusions is not planned. However, if an infusion reaction occurs, appropriate medication may be used as determined by the study investigator(s). If infusion reactions are observed, but review of the data suggests that dose escalation may continue, acetaminophen 500 to 1000 mg and/or an antihistamine may be administered orally 30 to 60 minutes prior to the start of infusion for subsequent patients/subjects.

The decision to implement premedication for infusions in subsequent cohorts will be made by the investigator and sponsor and recorded in the study documentation, along with the dose-escalation decision.

Any premedications given will be documented as a concomitant therapy (see Section 7.7).

#### **7.4.3.1. Management of Infusion Reactions**

There is a risk of infusion reaction with any biological agent; therefore, all patients/subjects should be monitored closely. Symptoms and signs that may occur as part of an infusion reaction include, but are not limited to fever, chills, nausea, headache, bronchospasm, hypotension, angioedema, throat irritation, rash, pruritus, myalgia, and dizziness. In the event that a significant infusion reaction occurs, the following guidance should be followed:

- The IP infusion should be slowed (for example, reduce infusion rate by 50% [for example, an infusion rate of 12 mL/h becomes 6 mL/h or slower]) or stopped, depending on the symptoms/signs present:
  - if slowed, the infusion should be completed at the slower rate, as tolerated
  - if determined by the investigator that the infusion should no longer continue, no further attempts to dose the patient/subject should be made
- Supportive care should be employed in accordance with the symptoms/signs
- If a patient/subject's infusion reaction is sufficiently severe to discontinue the infusion, subsequent infusions may be administered with premedication at the discretion of the investigator following agreement with the Lilly CRP or clinical pharmacologist

- If a patient/subject's infusion rate is reduced due to an infusion reaction, subsequent infusions may be administered at the discretion of the investigator following agreement with the Lilly CRP or clinical pharmacologist. If further infusions are administered, the infusion rate must not exceed the slowest rate used to complete the infusion when the infusion reaction occurred. Premedication may be administered at the discretion of the investigator
- If it is determined that the patient/subject should not receive further doses of IP, the patient/subject should complete AE and other follow-up procedures per Section 2 of this protocol.

## 7.5. Preparation/Handling/Storage/Accountability

All clinical trial materials provided to the investigator will be stored in a secure place and allocated and dispensed by appropriately trained personnel. The allocation and dispensation of the IP will be fully documented and verified by a second person. Detailed records of the amounts of the IP received, dispensed, and remaining at the end of the study will be maintained.

The investigator or designee must confirm appropriate temperature conditions have been maintained, as communicated by the sponsor, during transit for all IPs received and any discrepancies are reported and resolved before use of the study treatment.

Only participants enrolled in the study may receive IPs or study materials, and only authorized site staff may supply or administer IP. All IPs should be stored in an environmentally controlled and monitored (manual or automated) area in accordance with the labeled storage conditions with access limited to the investigator and authorized site staff.

The investigator, institution, or the head of the medical institution (where applicable) is responsible for study treatment accountability, reconciliation, and record maintenance (such as receipt, reconciliation, and final disposition records).

Investigational products will be supplied by Lilly or its representative, in accordance with current good manufacturing practices and will be supplied with lot numbers, expiry dates, and certificates of analysis, as applicable.

The logo consists of the letters 'CCI' in a large, bold, red sans-serif font, centered on a solid black rectangular background.

## 7.6. Treatment Compliance

The IP will be administered at the clinical site, and documentation of treatment administration will occur at the site.

## 7.7. Concomitant Therapy

In general, concomitant medication should be avoided. Use of chronic, stable doses of Thyroxine or hormone replacement therapy (estrogens/progesterones) is allowed in both healthy subjects and patients with psoriasis.

Acetaminophen (1 g, maximum 2 g/24 hours) may be administered at the discretion of the investigator for treatment of headache, etc. If the need for concomitant medication (other than acetaminophen) arises, inclusion or continuation of the patient/subject may be at the discretion of the investigator after consultation with a Lilly clinical pharmacologist or CRP. Any medication used during the course of the study must be documented.

Uses of nonlive (inactivated) vaccinations are allowed for all subjects. Use of live, attenuated vaccines is prohibited.

Patients in Part C who are on stable concomitant medication at the time of study entry should continue their regular, unchanged dose throughout the study and the extended follow-up period (up to Week 52). Concomitant therapies for treatment of psoriasis during the study are permitted only as outlined in [Table FFAA.7.1](#).

**Table FFAA.7.1. Permitted Medications for Treatment of Psoriasis**

Drug Class	As Needed	Chronic Use	Conditions for Use
Topical steroids	Yes	Yes	Topical steroids Class 6 [mild] or 7 [least potent] will be permitted for use limited to the face, axilla, and/or genitalia, as needed. These topical medications should not be used within approximately 24 hours prior to study visits.
Topical medications for psoriasis	No a	No	

a Exceptions: topical steroids will be permitted for use limited to the face, axilla, and/or genitalia.

Topical moisturizers/emollients may be used on nontarget lesions (that is, plaque psoriasis lesions that have not been or will not be biopsied) following the Day 1 visit.

## 7.8. Treatment after the End of the Study

Not Applicable.

## 8. Discontinuation Criteria

Patients/subjects discontinuing from the study prematurely for any reason must complete AE and follow-up procedures per Section 2 of this protocol.

### 8.1. Discontinuation from Study Treatment

Discontinuation of the IP for abnormal liver tests **should be considered** by the investigator when a patient/subject meets 1 of the following conditions after consultation with the Lilly-designated medical monitor:

- ALT or AST  $>5\times$  ULN for healthy subjects,  $8\times$  ULN for patients
- ALT or AST  $>3\times$  ULN for healthy subjects,  $5\times$  ULN for patients sustained for more than 2 weeks or
- ALT or AST  $>3\times$  ULN and TBL  $>2\times$  ULN or international normalized ratio  $>1.5$  or
- ALT or AST  $>3\times$  ULN with the appearance of fatigue, nausea, vomiting, right upper-quadrant pain or tenderness, fever, rash, and/or eosinophilia ( $>5\%$ )
- ALP  $>3\times$  ULN
- ALP  $>2.5\times$  ULN and TBL  $>2\times$  ULN
- ALP  $>2.5\times$  ULN with the appearance of fatigue, nausea, vomiting, right-quadrant pain or tenderness, fever, rash, and/or eosinophilia ( $>5\%$ ).

